9.1 Screening Phase

The Screening visit should be completed within a 24-hour period prior to randomization. The Screening procedures will be used to establish subject eligibility and Baseline characteristics for each subject. Following the signing of an ICF, the site staff will collect/perform the following:

- Demographics
- Medical history
- Physical examination
- Vital signs: body weight & height, body temperature, blood pressure, heart rate
- Review of inclusion/exclusion criteria
- Laboratory tests (blood):
 - hematology (includes coagulation)
 - chemistry
 - serum pregnancy test
- Laboratory tests (urine):
 - Urinalysis via dipstick with optional microscopic exam
 - Urine culture
 - Urine pregnancy test
- Concomitant medications (past 7 days)
- AEs since the signing of the ICF
 - Subject assessment of UTI signs and symptoms severity (UTISA questionnaire)

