3.1 Sample Size Considerations

Enrollment of a total of approximately 225 subjects is planned. The Bayesian posterior probability that the clinical success rate at the PTE Visit is within 0.10 of that of the nitrofurantoin group will be estimated for each omadacycline dose group. The target probability is 0.80. If the true underlying clinical success rates for the nitrofurantoin and omadacycline dose groups are 0.82, then the sample size of $N = 50$ per treatment has approximately 79% power/probability to yield the target probability ($N = 53$ per treatment for 80% power).

The sample size may be increased for a particular omadacycline dose group by changing the randomization ratio and/or dropping a dose group to achieve improved power/probability of achieving the target probability that clinical success rates for a dose group is within 0.10 of that of the nitrofurantoin group. If required to improve the precision of the interim or projected final

analyses estimates of response rates or posterior probabilities, sample size may be increased to a maximum sample size of 300 patients.

The decisions affecting changes of randomization to treatment groups, hence affecting total sample size, will be based on the recommendation of the DMC at interim analyses in an unblinded manner. Statistical details relevant to pre-defined decision rules for the DMC are documented in the DMC SAP⁽¹⁾.

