- Missing UTISA responses at baseline will be imputed with Day 1 responses.

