7.2 Primary Efficacy Endpoint Analysis

The primary efficacy endpoint is investigator's assessment of clinical response at PTE in the ITT population, as measured by the number of subjects in each treatment group.

The primary efficacy outcome is the percentage of subjects with an overall clinical success at the PTE Assessment in the ITT population. Each omadacycline treatment group will be compared to nitrofurantoin group for non-inferiority (pairwise). This non-inferiority test will be based on the lower limit of the 2-sided exact 95% confidence interval (CI).

The null and alternative hypotheses are as follows for overall clinical success:

$$H_0 : p_1 - p_2 \leq -\Delta \text{ and } H_1 : p_1 - p_2 > -\Delta,$$

where p_1 is the primary efficacy success rate in each of the omadacycline treatment group, p_2 is the primary efficacy success rate of nitrofurantoin group, and Δ is the non-inferiority margin of 10%. No multiplicity adjustment will be used to account for multiple doses being compared to levofloxacin.

To test the null hypothesis, a 2-sided 95% CI for the observed difference in primary outcome rates (omadacycline group minus nitrofurantoin group) will be calculated. If the lower limit of the 95% CI for the difference exceeds -10% , then the null hypothesis will be rejected and the non-inferiority of omadacycline to nitrofurantoin will be declared for that dose.

The number and percentage of subjects in each treatment group defined as an overall clinical success, failure and indeterminate (subjects with missing data or who are lost to follow-up) will be tabulated, as will the overall category combining failure and indeterminate.

In addition, 95% credible intervals will be provided for the difference in success rates using the modeling as follows. Assuming the likelihood for number of responders to have binomial distribution [$Y_i \sim \text{Bin}(n_i, p_i)$] and non-informative beta priors [$p_i \sim \text{Beta}(0.5, 0.5)$]. The posterior probability of non-inferiority will be computed as $P(p_{\text{OMC}} - p_{\text{N}} > -0.1 \mid \text{data})$ for assessment.

Additional sensitivity analyses are described in [Section 7.5.2](#).

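### The primary comparison in SAP 7.2 ignores scheduled baseline UTISA severity; a prespecified adjusted estimate beside it would recover a little precision at low cost

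*SAP*

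**What the plan says.** **Primary comparison.** SAP 7.2 takes the omadacycline minus nitrofurantoin difference in overall clinical success at PTE in the ITT population: "Each omadacycline treatment group will be compared to nitrofurantoin group for non-inferiority (pairwise"). The decision rule is "This non-inferiority test will be based on the lower limit of the 2-sided exact 95% confidence interval (CI"), and Δ "is the non-inferiority margin of 10" percentage points. A second calculation gives each arm a binomial likelihood with "non-informative beta priors", Beta(0.5, 0.5), and reports a 95% credible interval and the posterior probability that the difference exceeds -0.1. Neither calculation names a covariate or stratum.

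**Baseline severity.** The Screening list in Protocol 9.1 includes "Subject assessment of UTI signs and symptoms severity (UTISA questionnaire"). SAP 7.1.3 defines a severity total from 0 to 21, set to missing if fewer than 4 items are answered. SAP 5.1.2 adds: "Missing UTISA responses at baseline will be imputed with Day 1 responses". The visible uses are the baseline table (SAP 6.2) and the exploratory summaries (SAP 7.1.3 and 7.4.1).

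**Balance.** SAP 3.2 describes a blocked, centrally balanced sequence set out in IxRS specifications. It names no stratification factor.

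**Other modelling.** Protocol 12.5.1 promises further Bayesian modelling of the primary endpoint, and SAP 7.2 refers to sensitivity analyses in 7.5.2. The text of Section 7.5 is blacked out in the public copy.

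**The concern.** Success is the investigator's judgement that signs and symptoms have resolved far enough that no further antimicrobial is needed. How severe the symptoms were at entry is a natural candidate to predict that, and the questionnaire is already scheduled before treatment. If severity is prognostic, part of the scatter in the observed difference comes from chance differences in severity between arms, and a model could take that part out. The arms are small (225/5 = 45 if equal), four of them are compared with one control, and the results are meant to help choose regimens for later studies. What is at stake is modest: some precision, and some help in reading a dose difference that may partly reflect who happened to be in each arm.

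**Working it through.** **The plan's own figure.** SAP 3.1 states about 79% probability of success at 50 per arm ("If the true underlying clinical success rates for the nitrofurantoin and omadacycline dose groups are 0.82"; "The target probability is 0.80"). Exact enumeration of both binomials with Beta(0.5, 0.5) priors, counting success when P(difference > -0.10 | data) > 0.80, gives 69.2% at 50 per arm and 66.7% at 45. The stated figure is therefore not reproduced. That is a separate matter, and nothing below uses it.

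**Inputs.** From the documents: success rate p = 0.82 in every arm, 45 per arm, margin 10 points. Assumed: baseline severity X is standard normal, log-odds of success are linear in X, and the odds ratio per SD is 1.2, 1.5 or 2.0.

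**Step 1, unadjusted standard error.** sqrt(2 × 0.82 × 0.18 / 45) = 0.0810, or 8.1 points.

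**Step 2, share of variance explained.** R² = Var[p(X)] / (0.82 × 0.18), with the intercept set so that mean success is 0.82.

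**Step 3, what adjustment gains.** Adjusted SE = 8.1 × sqrt(1 - R²). Equivalent extra women per arm = 45 × [1/(1 - R²) - 1]. Power of the 95% interval test, by normal approximation, = Φ(10/SE - 1.96).

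**Step 4, the same quantity as a shift.** The 95% limit of the part of the difference due to severity imbalance is 1.96 × 8.1 × sqrt(R²). As a check by another route, the 95% limit of the imbalance itself is 1.96 × sqrt(2/45) = 0.413 SD. Multiplying by the average slope, ln(OR) × 0.1476 × (1 - R²), gives 1.1, 2.4 and 3.9 points.

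| OR per SD (assumed) | R² | Adjusted SE (points) | Extra women per arm | Power, from 23.4% | Shift at 95% limit (points) |
|---|---|---|---|---|---|
| 1.2 | 0.0049 | 8.08 | 0.2 | 23.5% | 1.1 |
| 1.5 | 0.0238 | 8.00 | 1.1 | 23.9% | 2.5 |
| 2.0 | 0.0666 | 7.83 | 3.2 | 24.8% | 4.1 |

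**Step 5, validity of the unadjusted analysis.** In simulations of two arms of 45 (4,000 trials at each odds ratio of 1, 1.5, 2 and 3), the mean unadjusted difference was within about 0.2 points of zero. Its Wald 95% interval covered 94–95%. The exact interval itself was not simulated.

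**Step 6, price of adjusting for nothing.** At OR 1, adjusted and unadjusted two-arm estimates still differed with an SD of 0.9 points, because the covariate effect has to be estimated. The SD of the estimate rose from 8.08 to 8.13 points. Fitting all five arms in one model left essentially no variance penalty.

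**Step 7, sensitivity of the posterior.** With 37/45 successes in both arms, P(difference > -0.10 | data) is 0.90. One fewer omadacycline success gives 0.83, and two fewer give 0.75. One woman is 1/45 = 2.2 points, so shifts of the size in the table can matter near the 0.80 target.

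**The case against.** The strongest reply is that this is an optional refinement of a sound analysis. The trial is a Phase 2 dose-finding study with nominal inference (SAP 5.1.4), and the unadjusted beta comparison is the one named in Protocol 12.5.1. Success is an investigator's judgement, not a change in UTISA, and indeterminate outcomes count as non-success in ITT. Both could weaken any link with baseline severity. The binding limit is arm size: about 23% power for the interval test at 45 per arm, with or without adjustment. All of this stands, and it keeps the point small.

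Four stronger readings are tempting, and the documents do not support them.

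- **A reader might infer that chance imbalance biases the comparison.** It does not. Under randomisation it is part of the 8.1-point SE.
- **A reader might count the shift as a harm on top of the lost precision.** Step 4 shows that they are one quantity: the shift is the explained variance, read at a chosen extreme.
- **A reader might take a shift of several points as established.** No passage says how strongly baseline UTISA predicts success.
- **A reader might conclude that every woman has a baseline total, or that no adjusted analysis is planned.** The first is only the schedule, since the SAP itself provides for missing values. The second cannot be confirmed or excluded while Section 7.5 is blacked out.

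Section 7.5 is labelled sensitivity analysis, so its content would not change the primary calculation visible in 7.2. An adjusted model there would meet most of this point.

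**Conclusion.** The point holds as a small, cheap improvement and not as an error. SAP 7.2 is valid as written but leaves unused a baseline measure that the trial already collects. The likely gain is a variance reduction of 0.5% to 6.7%, worth 0.2 to 3.2 women per arm and at most about 1.4 percentage points of power (23.4% to 24.8%). It rests on the assumed odds ratios of 1.2 to 2.0 per SD, equal arms of 45, a success rate of 0.82 and a logistic relation.

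One limit applies. The statement that the unadjusted difference is unbiased is for arms randomised side by side. Group 4 was added by Amendment 2, after a blinded review of the first 145 subjects, and SAP 7.2 does not say whether its control is restricted to women randomised in the same period. Severity adjustment would not remove calendar effects from that comparison.

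**What to change.** Keep the exact interval and the beta-binomial posterior in SAP 7.2, and prespecify beside them:

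- one logistic model across all five arms, with weak priors, arm indicators and baseline UTISA severity total;
- standardisation of each arm's success rate over the whole ITT population;
- the adjusted difference from nitrofurantoin, its 95% credible interval and P(difference > -0.10 | data).

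State a simple rule for subjects who still lack a baseline total after the Day 1 back-fill, for example the overall mean, so that no ITT subject drops out. Say also whether a back-filled Day 1 response must precede the first dose; Protocol 9.2.1 lists the questionnaire among Day 1 procedures without giving its timing. If Section 7.5 already contains this model, a cross-reference from 7.2 is enough.

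The cost is SAP wording and modest programming, with no new data. The downsides are that the adjusted result depends on a model and is not exact, that the gain is slight if severity is weakly prognostic, and that it does nothing for the small arm size.

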5.1.1 Adaptive Design

This is an adaptive dose-response finding study. Initially, subjects will be randomized (1:1:1:1:1) to five treatment groups. During the course of the study, a Bayesian analysis will be used to adaptively allocate new subjects to one of the treatment arms, conditional on the availability of primary efficacy endpoint data (investigator assessment of clinical response at PTE). When there is sufficient information available about the dose-response, results from the Bayesian analysis will be reviewed by a DMC to determine if enrollment in any

omadacycline treatment arms should be stopped or modified. Modifications to omadacycline dosing regimens/treatment arms may also be based on safety and tolerability.

Bayesian analyses will be conducted after efficacy data (investigator assessment of clinical response at PTE) are available for approximately 40, 80, and 100 subjects in order to:

1. Determine omadacycline dose group(s) that can be dropped from the trial, or
2. Modify the randomization ratios among the dose groups to improve the precision of the selected dose groups comparison of clinical success to that of the nitrofurantoin group.

Additional analyses may be carried out for the same two purposes. Response criteria are targeted toward estimating the probability that the clinical success rate (proportion of subjects) for each omadacycline dose group is within 10% of that of the nitrofurantoin group. If at the analyses, that probability falls below 30% for a particular dose group, recruitment for that dose group may be stopped or curtailed. If that probability exceeds 80% for a particular omadacycline dose group, recruitment for that dose group may be increased to improve the precision of the estimate.

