12.5 Primary Endpoint(s)

12.5.1 Efficacy Endpoint

The primary efficacy endpoint is the Investigator's assessment of clinical success at PTE in the ITT population. The number and percentage of subjects with an Investigator's assessment of clinical success, clinical failure and indeterminate response at the PTE visit will be determined by treatment group in the ITT population. Exact 95% confidence intervals will be determined for the point estimates of the clinical success rates in each treatment group.

A comparison of the clinical success rate at the PTE Visit between each omadacycline dose group and the nitrofurantoin group will be conducted using a beta distribution with an uninformative Bayesian prior distribution. Additional analyses on the primary efficacy endpoint will be performed using Bayesian modeling. Details are described in SAP.

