Indicated that additional analyses on the primary efficacy endpoint will be performed using Bayesian modeling.	An additional sensitivity analysis will be conducted on the efficacy endpoints to ensure improved interpretation and precision of estimates of efficacy analysis for dose selection.

A Randomized, Double-Blinded, Adaptive Phase 2 Study to Evaluate the Safety and Efficacy of Oral Omadacycline and Oral Nitrofurantoin in the Treatment of Female Adults with Cystitis

SUMMARY OF CHANGES

Product Name: Omadacycline (PTK 0796)

Study Number: PTK0796-UUTI-17201

Date and Version: Version 2, 29 October 2018

Protocol Section	Change
Synopsis	Reference to ECG removed as this is not a required study procedure and was included in error
Synopsis & Exclusion Criteria	Exclusion criterion #4 removed (in alignment with current FDA UUTI guidance) & marked as not applicable
Synopsis & Exclusion Criteria	Inclusion criteria #3 timepoint for onset of symptoms related to randomization clarified & Exclusion criterion #3 removed/marked as not applicable
Synopsis & Exclusion Criteria	Exclusion criteria #7 temperature parameters for fever slightly modified to align with current UUTI FDA Guidance
Synopsis & Exclusion Criteria	Exclusion criteria #10 updated to specify for a ' confirmed or suspected complicated UTI'
Study Procedures & Schedule of Assessments	Clarified timing of Day 1/Dose 1 PK collection
Efficacy Assessments	New section 8.7.1.3 added to collect Investigators Assessment of Clinical Response at Final Follow-up visit (per previously issued protocol clarification letter)
Concomitant Medication Assessments	updated title of eCRF page
Adaptive Design, Interim Analysis, Statistical Methods	probability % updated
Other Reportable Information	Removed references to paternal/male subject reporting as this is N/A for this study
UTISA	added reference to section 8.15.5 which discusses handling of worsening of disease under study and AE reporting
Multiple	Several section hyperlinks corrected
Schedule of Assessments	Typos corrected & footnotes G & U clarified

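### The 79% and 80% power stated for the 0.80 posterior target come out near 69% and 70%, and the 95% CI rule that declares non-inferiority in SAP 7.2 is unpowered, absent from the protocol and not listed as a change

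*SAP*

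**What the plan says.** **Sizing.** SAP 3.1, protocol 12.2 and the protocol synopsis size the trial on the posterior probability that a dose's clinical success rate at PTE is within 0.10 of nitrofurantoin's. "The target probability is 0.80". With true rates of 0.82 in every group, N = 50 "per treatment has approximately 79% power/probability to yield the target probability", and N = 53 is said to give 80%. Total enrolment is about 225 in five groups at 1:1:1:1:1. SAP 3.1 allows an increase to 300.

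**Primary analysis in the protocol.** Section 12.5.1 plans exact 95% confidence intervals for each group's own success rate. The comparison of each dose with nitrofurantoin "will be conducted using a beta distribution with an uninformative Bayesian prior distribution". There is no non-inferiority hypothesis, no interval for the difference and no final success threshold.

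**Primary analysis in the SAP.** Section 7.2 states null and alternative hypotheses with a 10% margin. "This non-inferiority test will be based on the lower limit of the 2-sided exact 95% confidence interval (CI". If that limit exceeds -10%, "the non-inferiority of omadacycline to nitrofurantoin will be declared for that dose". The beta-binomial model follows as an addition: "The posterior probability of non-inferiority will be computed as" P(p_OMC - p_N > -0.1 | data), for assessment, with no threshold.

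**Changes.** SAP 9, Changes from Protocol, says none apply. SAP 1 says the SAP prevails over the protocol and that differences will be explained in the study report.

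**The concern.** There are two separate problems.

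First, the power sentence gives its target, true rates and group sizes, so it can be checked, and it does not reproduce. A sponsor relying on it would think an equally effective dose reaches the target about four times in five, when the chance is nearer seven in ten.

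Second, the rule that declares a result is neither the criterion on which the trial was sized nor the comparison the protocol plans. A 95% lower limit is a much stricter bar than a posterior probability of 0.80 at the same margin. A reader who carries the 79% over to the declaration would badly misjudge what a missed declaration means: at these group sizes, a dose truly equal to nitrofurantoin usually fails the rule. The phrase exact interval also does not identify one method for a difference in proportions, and here the choice matters.

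**Working it through.** **Inputs.** True success 0.82 in both arms, target 0.80, and N = 50 and 53 per group (SAP 3.1). Margin 0.10, binomial likelihood, Beta(0.5, 0.5) priors and a one-sided posterior (SAP 7.2). 225/5 = 45 per group under equal allocation.

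**1. The stated 79% and 80%.** For each pair of counts (x, y), the posteriors are Beta(0.5 + x, 0.5 + n - x) for the dose and Beta(0.5 + y, 0.5 + n - y) for nitrofurantoin. Power is the sum of Bin(x; n, 0.82) × Bin(y; n, 0.82) over all pairs with P(p_OMC - p_N > -0.10 | x, y) ≥ 0.80.

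| N per group | Stated | Computed |
|---|---|---|
| 45 | – | 66.7% |
| 50 | 79% | 69.2% |
| 53 | 80% | 69.5% |
| 80 | – | 79.6% |
| 81 | – | 80.2% |

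Normal check at N = 50: SE = sqrt(2 × 0.82 × 0.18/50) = 0.0768, and 0.10/SE = 1.301. Phi(1.301 - 0.842) = 0.677, in line with the enumeration and well short of 0.79.

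**2. Other readings of the sizing sentence.** Section 3.1 does not state the prior or the direction, so I varied both.
- Beta(1, 1) priors: 69.2% at N = 50 and 71.2% at N = 53.
- Two-sided reading, P(|p_OMC - p_N| < 0.10) ≥ 0.80: 19.5% and about 24%.

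Neither gives 79% and 80%.

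**3. Power of the declaring rule.** I assume the lower 95% limit exceeds -0.10 exactly when an unconditional exact test of a difference of -0.10 rejects at one-sided 0.025. The p-value is maximised over the unknown common rate on a fine grid. Two usual orderings of the outcomes, with both true rates at 0.82, give:

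| N per group | Score-ordered exact | Raw-difference exact |
|---|---|---|
| 45 | 21.2% | 6.5% |
| 50 | 22.9% | about 8% |
| 53 | 23.9% | 8.2% |

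Normal check at N = 50: Phi(1.301 - 1.960) = 0.255, slightly above the score-ordered figure, as expected for an approximation that ignores discreteness.

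As an illustration, take 41/50 successes on nitrofurantoin. A dose then needs 44/50 for the score-ordered interval to clear -10%, and 47/50 for the raw-difference interval.

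**4. Group size for 80% power under the declaring rule** (normal approximation). n = (1.960 + 0.842)² × 2 × 0.82 × 0.18/0.10² = 7.85 × 29.52, or about 232 per group. The SAP caps the whole trial at 300. With 300/5 = 60 per group, the score-ordered power is about 27%.

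**The case against.** **Phase 2 and nominal inference.** The study is meant to help choose regimens, and SAP 5.1.4 makes all inferential statistics nominal. Low power for a confidence-interval rule is not an error in such a trial. That stands, and it limits the consequence. It does not correct a power figure that fails to reproduce, nor name the interval behind a rule that still declares non-inferiority.

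**The SAP may add analyses.** SAP 1 allows other analyses, gives the SAP precedence and promises explanation in the study report. SAP 7.2 also keeps the protocol's beta comparison. A reader might infer a concealed switch of the primary analysis; the documents do not support that. What remains is that SAP 9 is inaccurate. Protocol 12.5.1 does refer to the SAP for details, but directly after mentioning additional Bayesian modelling, not a frequentist test.

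**Unseen material.** The DMC SAP and the redacted sensitivity section were not available, so a sizing calculation with other settings cannot be excluded. Adaptive reallocation could also enlarge an arm: 100 on a dose against 50 on nitrofurantoin gives 77.6% for the 0.80 target. But the sentence quotes a fixed N per treatment.

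**Two stronger readings to resist.** A reader might treat 0.80 as a rival final success rule and count how often a dose would meet it yet miss non-inferiority. Neither document sets such a rule. The 0.80 is a sizing target and an interim trigger: "If that probability exceeds 80% for a particular omadacycline dose group, recruitment for that dose group may be increased". SAP 7.2 already makes the interval the declaring criterion and the posterior supplementary. A reader might also infer that the power was computed for a lower target and left behind, since the Version 2 change log records "probability % updated". That entry concerns superseded text and does not say which figure changed, so it proves nothing.

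**Conclusion.** Both parts hold, as a matter that should be fixed.

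(a) As written, the stated power is overstated by about 10 percentage points: roughly 69% at N = 50, 70% at N = 53 and 67% at N = 45, with about 81 per group needed for 80%. This assumes equal groups, true rates of 0.82, independent Beta(0.5, 0.5) priors and the one-sided posterior of SAP 7.2. Uniform priors and the two-sided reading do not rescue the figures.

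(b) The rule that declares non-inferiority is not in protocol 12.5.1, is not the criterion to which the stated power refers, and is not acknowledged in SAP 9. Its power at N = 50 is about 23% (score-ordered) or 8% (raw-difference), so the unnamed method alone changes it about threefold.

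The finding does not show that the interval rule is the wrong choice, or that the SAP lacks a decision rule. It shows that the rule's low power is undisclosed, so a missed declaration could be misread as evidence of inferiority.

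**What to change.** Before database lock:

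1. In SAP 3.1, restate the power for the 0.80 target as about 69% at N = 50 and 70% at N = 53 (67% at N = 45). If 0.80 with these priors was not the basis, correct the threshold or inputs and state them. Make the same correction in protocol 12.2 and the synopsis, or list it in SAP 9, so that the repair does not create a new difference between the documents.
2. In SAP 7.2, name the exact interval method. In SAP 3.1, state the non-inferiority rule's power for that method. In SAP 9, list the test as a change from protocol 12.5.1.
3. In SAP 7.2, label the posterior probability supportive, or state otherwise, and note that failing the interval rule at this power is not evidence of inferiority.

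The cost is wording and a recomputed power statement, with no new data, patients or change of allocation. The downside is a less favourable stated power and a little extra analysis work.
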